DATA ANALYSIS & STATISTICAL CONSIDERATIONS: For the *ex vivo* studies, conditions will be performed in triplicate and experiments will be independently replicated to ensure reproducibility. For the *in vivo* assessments of airway remodeling and fibrosis (bronchodilator reversibility on ¹²⁹XeMRI), we will compare biomarkers of fibrosis (e.g., trichrome or percent elastic fiber staining) between BD types (fixed and reversible airway segments) both within and between obese asthma groups (early onset, late onset and non-asthma control) using a repeated measures two-way ANOVA with appropriate distributional assumption. Main effects of BD type, obese asthma group and their interaction will be evaluated with repeating BD type within subject (random effect) with compound symmetry variance structure. If significant main effect differences are found, pairwise comparisons between BD types and obese asthma groups will be done using Tukey's post-hoc test. Assuming a 50% decrease in fibrosis between BD fixed and reversible types, a sample size of 10 per group provides our study with ≥80% power to detect an effect size of 0.53 within and 0.60 between groups, where effect size (*f*) is the size of the mean differences relative to the standard deviation and assumed correlation (*p*) within group of 0.30. A p-value <0.05 will be considered statistically significant and all analyses will be performed using SAS version 9.4 or higher (SAS Institute, Inc., Cary, NC). Blinding to conditions and tissue sources will occur across the experimental design. In particular, tissues samples (post-BD fixed and BD reversible tissue based on region) will be blinded to the individual performing the experiments and the individual assays. The key for the tissue samples will be maintained by the program statistician and un-blinding will occur during data analysis by the statistician.

Because of [name] conflict of interest related to ¹²⁹XeMRI, and as required by his Polarean management plan, data analysis and image analysis will be conducted by un-conflicted individuals.

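### Compound symmetry imposes one variance on fixed and reversible segments; if the SD rises with mean fibrosis, group comparisons within a segment type lose their 5% level

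*Combined protocol and SAP*

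**What the plan says.** The Data Analysis & Statistical Considerations section, repeated in the Statistical Methodology row of the synopsis, compares fibrosis biomarkers "using a repeated measures two-way ANOVA with appropriate distributional assumption". Segment type (BD fixed or BD reversible) is the repeated factor, "with repeating BD type within subject (random effect) with compound symmetry variance structure". The between-subject factor has three levels: early-onset asthma, late-onset asthma and controls. After significant main effects, "pairwise comparisons between BD types and obese asthma groups will be done" with Tukey's test. On the level, "A p-value <0.05 will be considered statistically significant".

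The sample size argument runs "Assuming a 50% decrease in fibrosis between BD fixed and reversible types", then "a sample size of 10 per group provides our study with" at least 80% "power to detect an effect size of 0.53 within and 0.60 between groups", with an assumed correlation "within group of 0.30". The effect size f is defined against a single standard deviation.

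The documents give no SD for either segment type, no check of equal variance, no transformation and no alternative covariance structure. They do not say whether the Tukey comparisons are of marginal means or of groups within a segment type. The synopsis adds that data are assumed missing at random and that likelihood-based methods then give valid estimates. None of the eligibility lists requires a participant to have both a fixed and a reversible defect.

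**The concern.** Compound symmetry has one variance and one correlation. The example outcomes, trichrome and percent elastic fiber staining, cannot be negative, and for such measures the spread often grows with the mean. If it does here, a model that pools the two variances uses too small an error variance in the type with more spread and too large a one in the other. The higher-spread type would be fixed segments if they carry more fibrosis, as the study hypothesizes. For a marker that is lower in fixed segments the roles swap.

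Group differences within fixed segments, the tissue of main interest, would then be declared too often, and real group differences within reversible segments would be missed. Incomplete pairs add a second route. Likelihood inference under missing-at-random data also needs the covariance to be right, and a participant without one defect type contributes only one observation.

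**Working it through.** **The plan's own power figures.** Inputs: 3 groups of 10 (N = 30), f = 0.60 between, f = 0.53 within, alpha 0.05 (taken as two-sided), noncentrality N f².
- Between: 30 × 0.60² = 10.8 on (2, 27) df gives 80.0%.
- Within: 30 × 0.53² = 8.43 on (1, 27) df gives 79.9%.

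Both match the stated 80% when the correlation is left out. Repeated-measures formulas with correlation 0.30 give 94.1% and 99.7%, still at least 80%. These figures rest on one SD, so they say nothing about the variance ratio.

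**Variance used under compound symmetry, complete pairs.** Let q = SD(reversible) / SD(fixed); q is an assumption. The model variance of one observation is var(subject mean) + var(difference)/4. The covariance cancels, leaving (SD_F² + SD_R²)/2. The ratio of true to model variance is
- fixed: k_F = 2 / (1 + q²)
- reversible: k_R = 2q² / (1 + q²)

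A nominal 5% comparison of two groups within one segment type has large-sample error 2[1 − Φ(1.96/√k)].

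| q | k_F | error, fixed | k_R | error, reversible |
|---|---|---|---|---|
| 1 | 1.00 | 5.0% | 1.00 | 5.0% |
| 0.85 | 1.161 | 6.9% | 0.839 | 3.2% |
| 0.7 | 1.342 | 9.1% | 0.658 | 1.6% |
| 0.5 | 1.600 | 12.1% | 0.400 | 0.2% |

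Simulation (40,000 replicates, Satterthwaite df) agrees at q = 0.5: 12.2% in fixed segments with groups of 10/10/10 and 11.9% with 20/20/10. Separate variances return the error to 4.9–5.1%. A three-group F test, or a Tukey family confined to fixed segments, runs at about 15%.

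**Power in reversible segments, q = 0.5.** A difference that gives 80% power with the correct variance lies 1.96 + 0.84 = 2.80 standard errors from zero. Compound symmetry moves the critical value to 1.96/√0.4 = 3.10. Power is Φ(2.80 − 3.10) = Φ(−0.30), about 38%; simulation with groups of 20/20/10 gives 39%.

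**Effect of the post-hoc rule, fixed segments, q = 0.5, complete pairs.**
- Tukey over all six cells: 6.1% for any false group difference within fixed segments.
- Significant group main effect required first: 3.0% for one pair, 4.6% for the F or Tukey test.
- Comparisons opened by a significant BD-type effect: 11.4–11.8% for one pair, so no protection.

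**The three model tests, complete pairs.** With two segment types, BD type and the interaction rest on within-subject differences and the group effect on subject means. Compound symmetry estimates both of those variances freely. All three tests stay at about 5% at q = 0.5.

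**Analysis scale.** With constant coefficient of variation (0.3, 0.5 or 0.8) and a halved mean, compound symmetry on the log scale gives 4.8–5.1% in both segment types.

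**Incomplete pairs.** REML fits, 1,500 replicates, groups 20/20/10, correlation 0.30, q = 0.5, half the participants with one type only, t test on N − 3 df, Monte Carlo error about 0.6 points.

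| Pattern | Test | Compound symmetry | Unstructured |
|---|---|---|---|
| More reversible-only | BD type | 8.7% | 6.5% |
| | group contrast, fixed segments | 14.5% | 6.0% |
| More fixed-only | BD type | 4.2% | 6.2% |
| | group contrast, fixed segments | 9.9% | 5.5% |

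Across plausible splits with half the pairs incomplete, the BD-type test under compound symmetry lies between about 3% and 9%. The missingness patterns are assumptions.

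**The case against.** The strongest reply is that the plan assumes a halved mean, not a halved SD. That stands. A reader might infer that the 50% decrease itself implies a 2:1 SD ratio, and so an error rate more than twice nominal. The documents do not support this: they give no SD by segment type, and at equal SDs there is no inflation. The single-pair error passes 10% only when the larger SD exceeds 1.56 times the smaller.

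Second, the clause on an appropriate distributional assumption leaves room for a log scale, which removes the problem under constant coefficient of variation. That also stands, but the plan does not commit to any scale.

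Third, group comparisons within a segment type are only one reading of the post-hoc sentence; comparing marginal means is as natural. Even on the first reading, six-cell Tukey or a required group main effect brings the rate to about 6% or below 5%. This stands as a limit on the size. It does not remove the point, because the plan fixes neither the family nor which main effect opens it, and the reversible-segment comparison stays over-conservative.

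Fourth, the bronchoscopy section plans sampling from both segment types, and no rate of incomplete pairs is given. The incomplete-pair figures are therefore illustrations. Still, eligibility does not secure both defect types, and controls are chosen for lack of bronchodilator responsiveness.

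**Conclusion.** The point holds in a conditional form. The plan names a structure that forces equal variances where its own hypothesis gives reason to doubt them, and it provides no check or alternative.

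If the SD rises with the mean on the raw scale, an unadjusted pairwise group comparison within fixed segments, not preceded by a group test, runs at about 7%, 9% or 12% for SD ratios of 0.85, 0.7 or 0.5. The reversible-segment counterpart runs at about 3%, 1.6% or 0.2%. The post-hoc rule decides how much of this reaches the reported results.

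A reader might also infer that the planned main-effect and interaction tests are invalid. With complete pairs they are not. With half the pairs incomplete, an assumed pattern, the BD-type test shifts moderately, to about 3% to 9%, in a direction that depends on which type is missing. The SD ratio, the raw scale and the missingness pattern are all assumptions that the documents neither state nor exclude.

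**What to change.** Replace compound symmetry with an unstructured 2x2 covariance within participant: separate variances for fixed and reversible segments, plus their covariance. Use Kenward-Roger degrees of freedom. With two segment types, heterogeneous compound symmetry is the same model. The change is worth making whichever analysis scale and post-hoc family are chosen, though stating both in the same paragraph would settle how far the error rates above apply.

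The cost is a change of SAP wording and one extra variance parameter, with negligible loss of precision if the variances prove equal. The simple N − 3 df used in the incomplete-pair check left the unstructured BD-type test at 6.2–6.5%, which is a reason to specify a small-sample adjustment. Kenward-Roger itself was not simulated here.

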Aim 1. Identify the pathology, structural cell profile (airway fibroblast and epithelial cell) and redox status corresponding to regional areas of fixed and reversible post-bronchodilator defects (BD) in obese asthmatics.

We hypothesize that post-BD fixed defects identified on ¹²⁹XeMRI correspond to sites of increased oxidant stress and airway remodeling and fibrosis. We will use ¹²⁹XeMR imaging to guide bronchoscopy sampling of airways in both BD fixed and BD reversible ventilation defects. We will relate the contribution of the oxidant milieu, structural cell phenotypes and histopathologic composition of airways to changes in ventilation defects observed on ¹²⁹XeMRI.

Aim 2. Define the cellular requirement for redox-mediated TGF-β signaling between airway epithelial cells and fibroblasts driving regional remodeling in obese asthma. We hypothesize that regions of fixed defects on ¹²⁹XeMRI are composed of airway fibroblasts that are more proliferative, invasive and fibrogenic than fibroblasts in BD reversible defects and respond to the increased oxidative milieu and TGF-β signaling. We will assess epithelial cell signaling, airway fibroblast migration/invasiveness, proliferation and extracellular matrix (ECM) protein secretion with *ex vivo* cell culture models. These assays will establish significant associations between airway epithelial signaling and fibroblast function, changes in airway ventilation, and asthma endotypes.

Aim 3 Define regional differences of spatial interactions of mesenchymal cells with epithelial cells in the airway submucosa.

3A - Determine how transcriptional profiles change between lean vs obese asthma and controls;

3B - Determine how transcriptional profiles change in BD fixed vs responsive regions in obese asthma.

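### Only a significant main effect opens the pairwise tests, so a significant interaction leads nowhere and a fixed–reversible difference confined to one endotype is often not examined

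*Combined protocol and SAP*

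**What the plan says.** The rule stands in DATA ANALYSIS & STATISTICAL CONSIDERATIONS and is repeated in the Statistical Methodology row of the synopsis.

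- Purpose: fibrosis markers are compared between fixed and reversible segments "both within and between obese asthma groups (early onset, late onset and non-asthma control").
- Model: a repeated-measures two-way ANOVA. "Main effects of BD type, obese asthma group and their interaction will be evaluated".
- Follow-up: "If significant main effect differences are found, pairwise comparisons between BD types and obese asthma groups will be done", by Tukey's test.
- Significance level: "A p-value <0.05 will be considered statistically significant".
- Power: "a sample size of 10 per group provides our study with" at least 80% for f = 0.53 within and f = 0.60 between groups, with a correlation of 0.30. No power is stated for the interaction.

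No other follow-up rule appears, and no within-endotype contrast is prespecified. Aim 2 in the protocol body expects its assays to link epithelial signalling with "fibroblast function, changes in airway ventilation, and asthma endotypes", so endotype differences are part of the stated purpose.

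**The concern.** The interaction is the term that says whether the fixed–reversible difference varies by endotype, yet it is absent from the trigger. If the difference exists in one endotype only, the segment-type main effect averages it with two groups in which it is zero, one of them the non-asthma controls. The average may not reach significance. If the group effect does not either, the plan as written gives no route to the within-endotype comparison, even when the interaction is significant.

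The condition also buys nothing. Tukey's test controls the familywise error over its own set of comparisons without a preceding overall test, so the main-effect requirement can only remove power.

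**Working it through.** **1. The plan's own figure.** Noncentral F with λ = f²N, N = 30, α = 0.05:
- between groups: 0.60² × 30 = 10.8, df 2 and 27, power 80.0%;
- within: 0.53² × 30 = 8.43, df 1 and 28, power 80.0%.

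The stated 80% is reproduced, but by formulas that do not use the correlation of 0.30. Repeated-measures formulas that do use it give 99.7% (within, N = 30), 71.3% (within, one group of 10) and 94.1% (between). The documents therefore do not fix the SD to which f = 0.53 refers.

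**2. Two readings of f = 0.53** (difference δ in units of the SD of one measurement):
- f = δ/(2 SD): δ = 2 × 0.53 = 1.06 SD;
- f = δ/SD of the paired difference, which is √(2 × (1 − 0.30)) = √1.4 = 1.183: δ = 0.53 × 1.183 = 0.63 SD.

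**3. Group sizes.** 10/10/10 from the power statement. The synopsis plans 15–20 per endotype and 10 controls, hence 15/15/10 and 20/20/10 (early, late, control).

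**4. Dilution of the main effect.** With δ in one endotype only, the equally weighted main effect has λ = (δ/3)² / (1.4 × Σ(1/n)/9) = δ² / (1.4 × Σ(1/n)), with df 1 and N − 3.

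| Sizes | δ (SD) | λ | Segment-type main effect significant |
|---|---|---|---|
| 20/20/10 | 1.06 | 1.124/0.28 = 4.01 | 50% |
| 20/20/10 | 0.63 | 0.393/0.28 = 1.40 | 21% |
| 10/10/10 | 1.06 | 1.124/0.42 = 2.68 | 35% |
| 10/10/10 | 0.63 | 0.393/0.42 = 0.94 | 15% |

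**5. Detection of the within-endotype difference.** Simulated with correlation 0.30, pooled error on N − 3 df, and Tukey over six cell means. Either main effect, segment type or group, may open the tests. *No shift* leaves the three group means equal. *Shift* raises only the fixed segments, so the affected group's mean rises by δ/2 and the group effect can open the tests as well. The last column is a planned contrast at two-sided 0.025 (noncentral t, noncentrality δ√(n/1.4)), the threshold of Holm's first step for two contrasts.

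| Sizes | δ (SD) | Tukey, no condition | With condition, no shift | With condition, shift | Planned contrast (noncentrality) |
|---|---|---|---|---|---|
| 20/20/10 | 1.06 | 84% | 49% | 65% | 95% (4.01) |
| 20/20/10 | 0.63 | 29% | 13% | 15% | 53% (2.37) |
| 15/15/10 | 1.06 | 68% | 40% | 50% | 87% (3.47) |
| 15/15/10 | 0.63 | 19% | 9% | 10% | 40% (2.05) |
| 10/10/10 | 1.06 | 43% | 26% | 30% | 68% (2.83) |
| 10/10/10 | 0.63 | 10% | 6% | 6% | 26% (1.68) |

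Smaller runs of 4,000 replicates agree within about two points.

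**6. Signal present but unused.** At 20/20/10 and 1.06 SD the interaction is significant in 77% of trials. It is significant while neither main effect is in 37% (no shift) or 20% (shift).

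**7. Difference shared by both asthma groups, 20/20/10.** At 1.06 SD, Tukey detects it in a given group in 84–85% without the condition and 83–84% with it, a loss of about 1 point. At 0.63 SD the figures are 28–29% and 25%, a loss of 3 to 4 points. Planned contrasts reach 95% and 53%, so nearly all of that gap is Tukey over six cells against two planned contrasts, not the condition.

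**8. Interaction added as a trigger.** At 20/20/10 and 1.06 SD in one endotype, Tukey detects the difference in about 83%, against 84% with no condition.

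**The case against.** Four points can be made for the plan.

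*The hypothesis is not endotype-specific.* The aims expect the fixed–reversible difference in obese asthmatics generally, and the power statement assumes a 50% decrease without limiting it to one endotype. If both asthma groups share the difference, the segment-type main effect is significant in about 97% of trials at 20/20/10 and 1.06 SD, and the condition is nearly free. This stands and limits the point to differences confined to one endotype. The plan nevertheless promises within-group comparison.

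*Either main effect opens the tests.* More fibrosis in the fixed segments of one endotype also raises that group's mean. This stands; it is why the ranges extend to 65% and 30%. A reader might infer that a one-endotype difference is usually missed. The documents do not support that in general: at 20/20/10, 1.06 SD and a mean shift it is found in 65% of trials. Where it is usually missed, at 10 per group or at 0.63 SD, Tukey without any condition also misses it in 57–90%, so the condition is only part of the cause.

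*The interaction is tested.* A varying effect would often show there. But the overall interaction test does not say which endotype differs or in which direction, and the plan has no rule for the next step. Nor does the text say that a significant interaction would go unreported; that would be an inference.

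*The wording may be loose.* The authors may count the interaction among the main effects. The preceding sentence names it separately, so one clarifying sentence is needed either way.

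A reader might also infer inflated error across markers, since the plan refers to "biomarkers of fibrosis (e.g., trichrome or percent elastic fiber staining"). That is a separate matter. The list is illustrative, the number of tests is unknown and results from the same patients are not independent, so no familywise figure is given here.

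**Conclusion.** The point holds, with medium confidence. The follow-up rule omits the interaction and can block the within-group comparison that the same section promises. For a difference confined to one endotype, the cost in detection is:
- 20/20/10: 19 to 35 points at 1.06 SD (84% against 65% or 49%) and 14 to 16 points at 0.63 SD (29% against 15% or 13%);
- 10 per group: 13 to 17 points at 1.06 SD (43% against 30% or 26%) and about 4 points at 0.63 SD (10% against 6%).

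These sizes rest on four assumptions: the SD behind f = 0.53, with both readings shown; a correlation of 0.30; either main effect opening the tests; and Tukey covering six cell means. The text does not define that family. If Tukey were meant only for the marginal means, no within-endotype comparison would be planned at all. When both asthma groups share the difference, the shortfall against planned contrasts belongs to the six-cell Tukey adjustment and should not be charged to the main-effect condition.

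**What to change.** Change the follow-up sentence in both places where it occurs.

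- **Minimum:** remove the main-effect condition, or state that a significant interaction also opens the within-group fixed–reversible comparisons. Define the set of means over which Tukey's test is applied.
- **Preferred:** prespecify fixed minus reversible in early onset and in late onset as planned contrasts, tested without a prior overall test and with Holm's method at 0.05. Name the difference between these two contrasts as the interaction contrast, and state its power. Keep Tukey, without the condition, for the remaining exploratory pairs.

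The preferred version removes both sources of loss, the condition and the six-cell adjustment. The cost is wording in the statistical section and one further power calculation. No additional patients, visits or samples are needed.

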We hypothesize that the scRNA sequencing performed on epithelial brushings in Aim 1 will identify differentially expressed proteins in the airway epithelial cell secretomes (85) of early and late onset obese asthma and obese non-asthma subjects, which drive differential fibroblast function. To perform this analysis, we will derive candidate proteins from pathway analysis in the epithelial brushings, correlate these to the secreted epithelial proteins and then confirm that pathways regulated by these proteins are active in either stimulating or suppressing fibroblast migration and invasion using transwell assays. Candidate genes in fibroblasts harvested from early and late onset obese asthmatics and non-asthma obese controls will be validated using RT-PCR. These studies have the potential to yield novel mechanistic insights into the pathogenesis of airway remodeling and fibrosis in obese asthma.

We hypothesize that post-BD fixed defects identified on ¹²⁹XeMRI in obese asthmatics correspond to regions of airway remodeling and fibrosis. ¹²⁹XeMRI imaging-guided bronchoscopic brushings and biopsies will be used to obtain primary airway epithelial cells and fibroblasts to model early onset obese asthma (T2 high disease) *ex vivo* in cell culture. Epithelial cells will be grown in triplicate at air liquid interface (ALI) in 6-well transwells (86) at 37°C in 5% CO₂ until fully differentiated with a mucociliary phenotype then challenged *in vitro* with 50 ng/mL IL-13 ± 20 ng/mL leptin for 24-48 hours in serum free media (34) to mimic physiologic conditions of the T2 high obese asthmatic *in vivo*. To model nonT2 disease in the late onset non-allergic obese asthmatic primary airway

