epithelial cells harvested from BD fixed and BD reversible ventilatory defects on $^{129}\text{XeMRI}$ will be grown in triplicate in transwells at ALI and challenged with 200 ppm ozone (O_3) for 1 hour \pm 20 ng/mL leptin (O_3 dose and timing are based on prior work). In T2 high disease, $\text{TGF}\beta 1$ is upregulated and associated with eosinophil burden and asthma severity(89-91). $\text{TGF}\beta 1$ mRNA expression is also upregulated by O_3 in human fibroblasts (92). These experiments will allow us to determine the contribution of airway epithelial cells from post-BD fixed and post-BD reversible regions on $\text{TGF}\beta 1/2$ expression and apical reactive oxygen species (ROS) production (DCFH-DA, Cell BioLabs, Inc.). Basolateral cell supernatants will be assessed for secreted proteins (85, 93) to gain insight into which proteins are potentially involved in ECM degradation, matrix organization, and cell-cell interactions and how these are altered in the different asthma endotypes.

Primary airway fibroblasts obtained by endobronchial biopsy from post-BD fixed and post-BD reversible regions will be challenged with 50 ng/mL IL-13 \pm 20 ng/mL leptin (T2 high disease) vs 200 ppm ozone \pm 20 ng/mL leptin (non-T2 disease), respectively. Cell culture media will be assessed for ROS production (DCFH-DA, Cell BioLabs, Inc.) and specific secretion of $\text{TGF}\beta 1/2$, IL-13, elastin, and Type I collagen ($\text{Col1}\alpha$) (ELISA, R&D Systems) and fibroblast secretome to discern relative expression levels of ECM proteins as well as matrix metalloproteinases (MMPs) and tissue inhibitors of metalloproteinases (TIMPs), which are important for pro-fibrotic airway fibroblast functions (29, 31, 34). Fibroblast invasion, proliferation and migration will be assessed using previously described methods (34, 74). These studies will allow us to determine the fibroblast specific responses contributing to VDP heterogeneity.

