Primary airway epithelial cells and fibroblasts will be grown in co-culture and challenged with either 50 ng/mL IL-13 \pm 20 ng/mL leptin for 24-48 hours or 200 ppm O_3 \pm 20 ng/mL leptin for 1 hour to mimic early (T2 high) vs late (non-T2) onset obese asthma. ROS production and gene expression in airway epithelial cells will be measured and fibroblast invasion, proliferation and migration assessed as described above. To then determine if airway fibroblast functions (invasion vs. proliferation vs. migration) are dependent on oxidative stress, we will incubate cells for 4 hours with different concentrations (1, 3, 10 mM) of N-acetylcysteine (NAC) to alter the oxidative milieu. Cells will then be washed and incubated with 10 μM DCFH-DA (2',7'-dichlorodihydrofluorescein diacetate dye; Molecular Probes) in culture media for 30 min. Cells are then analyzed for intracellular ROS production by flow cytometry. Studies will be repeated using different $\text{TGF}\beta$ (SB431542; Stem Cell Technologies and LY-364947; Sigma Aldrich) and Nox4 (GKT137831; Medkoo Biosciences, Inc) inhibitors to determine if fibroblast function and oxidative milieu are dependent on $\text{TGF}\beta$ signaling and/or Nox4 expression/activity.

Both epithelial cells and fibroblasts produce $\text{TGF}\beta 1$ and ROS under profibrotic conditions (76). We hypothesize that airway post-BD fixed regions on $^{129}\text{XeMRI}$ are comprised of a subset of fibroblasts that are aggressively more invasive, highly proliferative and more pathogenic than fibroblasts from post-BD reversible regions. To determine if the changes in regional remodeling and fibrosis are cell specific, BD reversible epithelial cells will be grown in co-culture with BD fixed fibroblasts and vice versa, epithelial cells from BD fixed regions will be grown in co-culture with fibroblasts from BD reversible regions. Cells will be challenged with 50 ng/mL IL-13 + 20 ng/mL leptin or 200 ppm O_3 \pm 20 ng/mL leptin as described in Aim 2.1. Endpoints to be measured include fibroblast functional assays (invasion, proliferation and migration) and gene and protein expression (Nox4, $\text{TGF}\beta 1/2$, IL-13, elastin and type 1 collagen) and ROS production.

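### IL-13 secretion is to be read by ELISA in medium already dosed with 50 ng/mL IL-13, so that one readout is uninterpretable in the IL-13 wells; the unchallenged control and the allocation of challenges also need to be written down

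*Combined protocol and SAP*

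**What the plan says.** All of this is in the combined protocol and SAP, in the ex vivo paragraphs under DATA ANALYSIS & STATISTICAL CONSIDERATIONS.

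- **Fibroblast challenge.** "Primary airway fibroblasts obtained by endobronchial biopsy from post-BD fixed and post-BD reversible regions will be challenged with 50 ng/mL IL-13", with or without leptin, for T2-high disease, against 200 ppm ozone, with or without leptin, for non-T2 disease. The sentence ends with the word *respectively*.
- **Readout.** "Cell culture media will be assessed for ROS production" and for specific secretion of TGF-β1/2, "IL-13, elastin, and Type I collagen". The method given is "ELISA, R&D Systems".
- **Co-culture.** Epithelial cells and fibroblasts are grown together and given either IL-13 or ozone "to mimic early (T2 high) vs late (non-T2) onset obese asthma". In the experiment that swaps fixed and reversible regions, IL-13 gene and protein expression is again an endpoint, and one of the challenges is again 50 ng/mL IL-13.
- **Epithelial models.** IL-13 for 24-48 hours represents T2-high disease. The ozone experiment opens "To model nonT2 disease in the late onset non-allergic obese asthmatic primary airway" and applies ozone for 1 hour to cells from both fixed and reversible defects. The secreted proteins are meant to show "how these are altered in the different asthma endotypes".
- **Controls.** Conditions are run in triplicate and independently replicated. Leptin is the only factor written as present or absent. No vehicle or filtered-air condition is listed, and the N-acetylcysteine series is 1, 3 and 10 mM with no zero level.

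**The concern.** An ELISA on conditioned medium measures the IL-13 present, whatever its source. If the medium was dosed with IL-13 and nothing removes it, the assay mostly measures the dose. The ozone wells have no added IL-13, so a T2-high versus non-T2 comparison of this analyte would come out high on the IL-13 side by construction.

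Two gaps in the same paragraphs affect other readouts. A response to challenge needs an unchallenged reference from the same donor, and none is stated. The text also leaves open which cells receive which challenge. If the challenge follows the donor's endotype, a difference between endotypes cannot be told apart from a difference between reagents.

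Redox-mediated TGF-β signalling (Aim 2) is one of the listed primary outcomes, and only two or three biopsies per segment go to fibroblast culture. Cells used in a layout that cannot answer the question are not recovered at the analysis stage.

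**Working it through.** The plan states no figure for this readout, so there is none to reproduce. The in vivo power statement (10 per group) concerns tissue histology and has no bearing here.

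**1. How much of the reading is reagent?**

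Inputs:
- Added IL-13, from the plan: 50 ng/mL × 1,000 = 50,000 pg/mL.
- Secreted IL-13, *s*: not given. Assumed range 10 to 5,000 pg/mL.
- Assumed: the added IL-13 persists to sampling and the assay detects it.

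Reagent share = 50,000 / (50,000 + *s*):

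| *s* (pg/mL, assumed) | Calculation | Reagent share |
|---|---|---|
| 10 | 50,000 / 50,010 | 99.98% |
| 100 | 50,000 / 50,100 | 99.8% |
| 1,000 | 50,000 / 51,000 | 98.0% |
| 5,000 | 50,000 / 55,000 | 90.9% |

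**2. Could a difference in secretion still be seen on top of that background?**

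Take the plan's triplicates and an assumed assay coefficient of variation (CV) of 5-10%. The 95% noise on a difference between two triplicate means is about 1.96 × 50,000 × CV × √(2/3).

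- CV 5%: 1.96 × 2,500 × 0.8165 ≈ 4,000 pg/mL.
- CV 10%: 1.96 × 5,000 × 0.8165 ≈ 8,000 pg/mL.

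Secretion of 1,000 pg/mL or less lies well inside that noise. At 5,000 pg/mL it clears the noise only at the lower CV.

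**3. How far does this depend on persistence?**

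At *s* = 1,000, the reagent share falls to one half only if residual added IL-13 is down to 1,000 pg/mL, a loss of 49,000 / 50,000 = 98%. Partial loss does not rescue the readout either. A difference of 1,000 / 50,000 = 2% of the dose in how much IL-13 two cultures take up or degrade would look like a 1,000 pg/mL difference in secretion.

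**4. Which readouts are affected?**

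Only IL-13 protein in IL-13-dosed medium. TGF-β1/2, elastin, collagen I, MMPs and TIMPs, ROS, Nox4, invasion, proliferation and migration are not the added substance. IL-13 mRNA does not measure added protein, and the ozone wells contain none. The co-culture text does not say whether protein is read in medium or lysate; the calculation applies to medium.

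**5. Who receives which challenge? Three readings of the same text.**

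| Reading | Support in the text | Consequence |
|---|---|---|
| Each donor's cells receive both challenges, as disease models | The verbs are to model and to mimic; co-cultures receive either challenge | No aliasing |
| Challenge follows donor endotype | IL-13 is labelled early onset/T2-high, ozone late onset/non-T2 | Endotype is aliased with stimulus. The within-donor fixed versus reversible contrast survives. Cells from the 10 obese controls have no assigned challenge |
| *Respectively* pairs fixed region with IL-13 and reversible region with ozone | Word order of the fibroblast sentence only | The fibroblast region contrast is aliased with stimulus |

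The third reading sits badly with its neighbours: epithelium from both regions receives ozone, and the region-swapped co-cultures may receive either challenge.

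**The case against.** The strongest reply is that this is one analyte in one challenge arm. That is correct. A reader might infer that Aim 2 as a whole measures the stimulus and not the cells; the documents do not support this. Aim 2's stated hypothesis is fixed versus reversible region. If both regions of a donor receive the same challenge, which is explicit for ozone on epithelium, that contrast still reads the cells. The leptin, N-acetylcysteine and inhibitor contrasts do not depend on endotype allocation either.

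A reader might also infer that stimulus is fully confounded with the compared factor however the text is read. That ignores the disease-model reading, under which nothing is aliased. Pairing *respectively* with region is strained, because the word directly follows two disease labels. The wording is ambiguous; it does not set a rule.

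The contrast of 24-48 hours with 1 hour does not quantify bias. Those times are given for epithelium and co-culture, not for fibroblasts alone. Harvest time is not stated, and a gas exposure need not match a soluble cytokine in length.

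On controls, a laboratory may well run vehicle wells as routine, and assay details rest on cited methods. The Aim 1 work includes passage-0 staining, RNA and protein, sorting of fresh tissue and sequencing of brushings, with no challenge mentioned. So the missing control is a gap in the text, not evidence that none will be run. Those Aim 1 data describe phenotype and expression, though, and do not supply unchallenged secretion or function.

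None of this answers the IL-13 point. A wash is written before the ROS dye step, but no wash, medium change or blank is written before the IL-13 reading.

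**Conclusion.** The IL-13 secretion readout is wrong as written. In wells dosed with IL-13, added cytokine makes up 98% or more of the reading if cells secrete up to 1,000 pg/mL. That rests on three assumptions: the secreted level, persistence of the dose, and its detection by the assay. Under them, IL-13 protein cannot be interpreted in those wells or compared with the ozone wells.

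Two further matters are gaps to close, not demonstrated errors. The secretion and functional assays have no stated unchallenged control, and the allocation of challenge to donor and region is unclear. Aliasing of stimulus with endotype is conditional: it arises only if challenge is assigned by donor endotype.

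The point does not touch participant procedures or the powered histology analysis.

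**What to change.** 1. **IL-13 protein.** Remove it as an endpoint in IL-13-challenged wells and report IL13 mRNA there; gene expression is already a planned co-culture endpoint. Alternatively, measure IL-13 protein only after a wash into fresh medium, against a cell-free IL-13 blank taken through the same steps. Removing it is essentially free.
2. **Allocation.** Reword the fibroblast sentence so that fixed- and reversible-region cells from the same donor clearly receive the same challenge or challenges. This is an edit only.
3. **Control.** State a same-donor unchallenged condition (vehicle for IL-13, air for ozone) for the secretion and functional assays.
4. **Interpretation.** If challenge is assigned by donor endotype, say so, and state that between-endotype differences will not be attributed to the cells.

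The cost is a few extra wells per donor and region, from cells that are scarce, which leaves fewer for the leptin and inhibitor experiments. No extra participant procedure is needed. Giving both challenges to all groups, or fixing one common harvest time, would support more comparisons, but these are trade-offs for the investigators given cell yield.
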